2.10.1.4 Handling of missing values/censoring/discontinuations

The above analysis will be performed using all available data under the assumption that the probability of missing values of total LBM (kg) are independent of unobserved assessments (missing at random [MAR]). Therefore, the missing values will not be imputed for the primary analysis.

2.10.1.5 Sensitivity analyses

The following sensitivity analyses are planned:

As a sensitivity analysis, the primary analysis (using the same MMRM specified in [Section 2.10.1.3](#) [Statistical model, hypothesis, and method of covariate analysis]) will be repeated for those patients who are part of the Total LBM Week 24 Completers FAS Analysis Subset (as referenced in [Section 2.7](#) [Analysis Sets]).

Missing value imputation: For this sensitivity analysis, “missing not at random” (MNAR) is assumed meaning that missingness depends on the observed and unobserved data. Suppose that patients in the bimagrumab treatment groups who prematurely discontinue from the study due to an AE, death (D) or unsatisfactory therapeutic effect (UTE) behave like placebo treatment group patients after study discontinuation. This assumption implies that the drug effect diminishes once bimagrumab treatment group patients discontinue from the study. To perform this analysis, a Bayesian multivariate normal imputation model using non-informative priors is fitted to the repeated total LBM (kg) assessments at Baseline, Week 12 and Week 24 for all placebo patients. Based on this model, the conditional distribution of missing data given the observed data can be used to create multiple imputations for the missing values of patients in the bimagrumab treatment groups who discontinue from the study due to AEs, D or UTE.

Missing data for all other patients will be imputed under a MAR assumption i.e. missing data are conditional on the treatment information for the repeated total LBM (kg) assessments at Baseline, Week 12 and Week 24. More information on this can be found in [Section 3.11.2](#) (Pattern mixture model).

2.10.1.6 Supportive analyses

Per protocol analysis

The primary efficacy analysis (excluding sensitivity analyses) will be repeated for the PP analysis set as confirmation of the primary analysis results.

Dose-response modeling

Multiple comparison procedure – modeling

In addition, for all patients assigned to FAS, dose-response modeling will be performed using the multiple comparison procedure – modeling (MCP-Mod) approach which considers the following models:

1. Three-parameter Emax: $f(d) = E_0 + E_{max}d/(ED_{50} + d)$.
2. Sigmoidal Emax with $h = 3.5$: $f(d) = E_0 + E_{max}d^{3.5}/(ED_{50}^{3.5} + d^{3.5})$.
3. Exponential: $f(d) = E_0 + E_1 \exp\left(\frac{d}{\delta}\right) - 1$.
4. Linear: $f(d) = E_0 + \beta * d$.

Where d is the dose level, ED_{50} the dose that gives 50 percent of the maximum effect, h the Hill coefficient; δ and β the rate of change for the exponential and linear models respectively, E_0 the basal effect at $d = 0$ and E_1 the scale parameter in the exponential model.

In the MCP-Mod approach, all models listed above will be averaged in order to estimate the median dose for a given targeted response via inverse prediction along with associated 95% intervals using a bootstrap re-sampling method (repeated 1000 times). The analyses will always be performed using the MCP-Mod function of R software.

For the contrast test the guesstimates below will be assumed, in order to model a wide range of plausible scenarios for this drug. As mentioned above, a Hill coefficient of 3.5 was used for the sigmoidal Emax models as this better reflects the expected dose-response (as we are expecting the same efficacy of [placebo and bimagrumab 70 mg] and [bimagrumab 210 mg and 700 mg]). The guesstimates were independently chosen, hence the exponential δ is not related to the ED50 of the other models.

Model	Guesstimate
Emax1	ED50 = 105
Emax2	ED50 = 210
SigEmax1	ED50 = 105
SigEmax2	ED50 = 210
Exponential	$\delta = 300$

[figure not shown]
Non-standardized sigmoidal Emax model

Since the design of this study is limited to having only three active doses, another dose-response sigmoidal Emax model will also be considered which allows for estimation of the Hill coefficient (h). In this model, the fixed dose of 700 mg, 210 mg, and 70 mg for each patient will be normalized by their Baseline weight in kg (i.e. the fixed dose will be divided by the Baseline weight) to form a mg/kg dose regressor. The specific model to be applied to the mg/kg regressor will be the non-standardized sigmoidal Emax model. The mean dose-response and associated asymptotic 95% confidence intervals (i.e. fiducial intervals) will be provided using the inverse prediction approach again.

The non-standardized sigmoidal Emax model is parameterized as follows:

$$f(d) = E_0 + E_{max}d^{3.5}/(ED_{50}^{3.5} + d^{3.5}).$$

In choosing which dose-response model to select for estimating dose as well as characterizing the entire response profile, the MCP-Mod approach is the default under the rule of parsimony, provided it fits the data well and results in intervals for estimating doses that are smaller than the 4-parameter Emax model.

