9.4.4 Supportive analyses

As supportive analysis, the primary analyses will be repeated using the PP analysis set.

In addition, dose response modeling will be performed using the MCP-Mod approach, which considers the following models:

1. Three parameter Emax: $f(d) = E_0 + E_{max}d / (ED_{50} + d)$
2. Sigmoidal Emax with $h=2$: $f(d) = E_0 + E_{max}d^h / (ED_{50}^h + d^h)$
3. Exponential: $f(d) = E_0 + E_1 \exp(d/\delta) - 1$
4. Linear: $f(d) = E_0 + \beta * d$

Where d is the dose level, ED_{50} the dose that gives 50 percent of the maximum effect, h the hill coefficient; δ and β the rate of change for the exponential and linear models respectively, E_0 the basal effect at $d=0$ and E_1 the scale parameter in the exponential model.

In the MCP-Mod approach, all statistically significant models listed above will be averaged in order to estimate the median dose for a given targeted response via inverse prediction along with corresponding 95% intervals using a bootstrap re-sampling method.

Since the design of this study is limited to having only 3 active doses, another dose response sigmoidal Emax model will also be considered which allows for estimation of the Hill coefficient (h). In this model, the fixed dose of 70 mg, 210 mg, and 700 mg from each patient will be normalized by their baseline weight in kg (i.e., the fixed dose will be divided the

baseline weight) to form a mg/kg dose regressor. The specific model to be applied to the mg/kg regressor will be the non-standardized sigmoidal Emax model. The mean dose response and corresponding asymptotic 95% confidence intervals (i.e., fiducial intervals) will be provided using the inverse prediction approach again.

The non-standardized sigmoidal Emax model is parameterized as follows:

$$f(d) = E_0 + E_{max}d^h / (ED_{50}^h + d^h)$$

In choosing which dose response model to select for estimating dose as well as characterizing the entire response profile, the MCP-Mod approach is the default under the rule of parsimony, provided it fits the data well and results in intervals for estimating dose that are smaller than the 4 parameter Emax model.

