2.14 Changes/Clarifications from the Planned Statistical Analysis in Protocol

The following changes/clarifications from analyses planned in the protocol include:

- Protocol amendment 3 states that for the Week 24 analyses treatment, visit, treatment date, region, baseline LBM and the two interaction terms treatment*visit and baseline LBM*visit will be included in the model. Instead a complete model will be used including two more interaction terms, region*visit and treatment date*visit. The motivation for including these is that both are randomization strata and important to be part of the model. This should also not cause any concerns in terms of convergence.
- Protocol amendment 3 states that the secondary variable is gait speed (sec). However, instead derived gait speed (m/sec) will be used in the analyses. It is the speed (m/sec) at which the 4-meter course is completed and is derived by dividing 4 meters (m) by the time (sec) to complete the course.
- Regression analyses (simple and multiple), which are not described in protocol amendment 3, will be included to evaluate potential exploratory factors affecting the patient outcomes.
- MCP-MOD: Hill coefficient for the sigmoidal Emax model changed from 2 to 3.5 as this better reflects the expected dose-response (as we are expecting the same efficacy of [placebo and bimagrumab 70 mg] and [bimagrumab 210 mg and 700 mg]). Guesstimates for all models were also included.
- Protocol amendment 4 states the inclusion of responder endpoints and logistic regression analysis related to this.
- Changes to subgroup and by-group presentations in of [Table 2.2](#) (see [Section 2.6](#) [Subgroups])

- Change to epoch presentation. Clarity in terms of the epochs per treatment and post-treatment versus analyses.

3 Clinical Study Report - Appendix 16.1.9 Documentation of statistical methods

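### SAP 2.10.1.6 describes a dose-response model that estimates the Hill coefficient but prints it fixed at 3.5, and it drops the significance condition from MCP-Mod averaging; SAP 2.14 declares neither change

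*SAP*

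**What the plan says.** **The supplementary model.** Protocol 9.4.4 adds to MCP-Mod a sigmoidal Emax model on dose divided by baseline weight. It gives the reason as "another dose response sigmoidal Emax model will also be considered which allows for estimation of the Hill coefficient (h") and prints the model as "E_0 + E_{max}d^h / (ED_{50}^h + d^h"), with the exponent left as a parameter.

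SAP 2.10.1.6 repeats the sentence ("another dose-response sigmoidal Emax model will also be considered which allows for estimation of the Hill coefficient (h")) but prints "E_0 + E_{max}d^{3.5}/(ED_{50}^{3.5} + d^{3.5"). Its selection rule keeps MCP-Mod as the default provided it fits well and "results in intervals for estimating doses that are smaller than the 4-parameter Emax model".

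**The declared change.** SAP 2.14 lists "MCP-MOD: Hill coefficient for the sigmoidal Emax model changed from 2 to 3.5 as this better reflects the expected dose-response". The reason given in 2.10.1.6 is that "we are expecting the same efficacy of [placebo and bimagrumab 70 mg] and [bimagrumab 210 mg and 700 mg"].

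**Averaging.** Protocol 9.4.4 averages the statistically significant MCP-Mod models. SAP 2.10.1.6 says that "all models listed above will be averaged in order to estimate the median dose for a given targeted response". SAP 2.14 has no entry for this. SAP 2.10.2.5 applies the same approach to gait speed and SPPB.

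**The concern.** A programmer cannot follow both the prose and the equation in SAP 2.10.1.6. With the exponent fixed, the model no longer does the one thing it was added to do. Its target-dose interval then leaves out uncertainty about steepness. The selection rule uses interval width to decide whether MCP-Mod is kept, so a comparator that is too narrow tilts the choice.

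On averaging, the contrast test is still run (SAP 2.10.1.6 and 3.11.3), but the SAP no longer makes a target dose depend on it. A dose could be reported where no dose-response signal was shown.

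Finding the Phase 3 dose is a stated purpose of the trial (protocol synopsis), and the 35-patient 70 mg arm serves only dose-response modelling (protocol 3.3 and 9.7).

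**Working it through.** **Step 1: count the free parameters.**

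| Source | Free parameters | Count |
|---|---|---|
| Protocol 9.4.4 equation | E0, Emax, ED50, h | 4 |
| SAP 2.10.1.6 prose and label | E0, Emax, ED50, h | 4 |
| SAP 2.10.1.6 equation | E0, Emax, ED50 | 3 |

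The 2.14 entry cannot cover this model. It describes a move from 2 to 3.5 under the MCP-Mod label, and the supplementary model never had h=2.

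**Step 2: how much the exponent changes the curve.** Share of Emax = d^h/(ED50^h + d^h) at 70, 210 and 700 mg, using the SAP's ED50 guesstimates:

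| ED50 | h=1 | h=2 | h=3.5 |
|---|---|---|---|
| 105 mg | 0.400, 0.667, 0.870 | 0.308, 0.800, 0.978 | 0.195, 0.919, 0.999 |
| 210 mg | 0.250, 0.500, 0.769 | 0.100, 0.500, 0.917 | 0.021, 0.500, 0.985 |

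The h=1 column is the ordinary Emax shape, which is itself among the SAP's MCP-Mod candidates.

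**Step 3: coverage of the target-dose interval.** There were 2,000 simulated trials per scenario.

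- From the documents: 70/35/70/70 patients; weight 66 ± 12 kg (protocol 3.3), floored at the 35 kg entry limit; effect 1.0 kg and SD 1.0 kg (protocol 9.7); ED50 105 and 210 mg, which at 70 kg is 105/70 = 1.5 and 210/70 = 3.0 mg/kg.
- Assumed: target 0.5 kg; the 1.0 kg effect reached at 10 mg/kg; when estimated, h bounded to 0.3–10.
- Method: nonlinear least squares, with a delta-method 95% interval for log target dose.

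| True h | ED50 105 mg: fixed vs free | ED50 210 mg: fixed vs free | Fixed/free median interval length (log scale) |
|---|---|---|---|
| 1 | 74 vs 93% | 50 vs 85% | 0.45–0.50 |
| 2 | 77 vs 86% | 90 vs 92% | 0.68–0.77 |
| 3.5 | 89 vs 83% | 96 vs 96% | 0.94–0.97 |

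A 0.7 kg target or 15% dropout (the SAP's figure) leaves the pattern unchanged: at h=1, coverage is 50–75% with h fixed against 85–93% with h free. For an assumed 2.0 kg effect with the protocol's meaningful 1.0 kg as target, h=1 gives 82 vs 95% (ED50 105 mg) and 20 vs 95% (210 mg). Smaller repeat runs of the main scenarios agreed to within about 6 points.

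**Step 4: averaging rule.** Share of trials in which no candidate is significant, using optimal contrasts for the five guesstimate shapes plus linear, critical value 2.27 (one-sided 2.5%) or 1.96 (one-sided 5%), and 40,000 trials:

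| Standardised effect | One-sided 2.5% | One-sided 5% |
|---|---|---|
| LBM plan, 1.0/1.0 = 1.0 | 0% | 0% |
| SPPB plan, 1.0/1.5 = 0.67 | 1–2% | 0–1% |
| Gait plan, 0.15/0.25 = 0.6 | 2–6% | 1–3% |
| Low end of meaningful gait range, 0.1/0.25 = 0.4 | 25–35% | 16–24% |

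In the no-signal trials at 0.4 SD, averaging all models (AIC weights assumed) still reaches the target within 0–700 mg in 69–72% for a 0.2 SD target, 20–25% for 0.3 SD and 0% for 0.4 SD.

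**The case against.** The strongest reply is that the exponent is a slip which the documents largely resolve. The SAP sentence, the 4-parameter label, the protocol sentence and the protocol equation all point to h free. Only one formula disagrees, and it matches the second MCP-Mod candidate. SAP section 1 also says analysis follows protocol Section 9. A carry-over is indeed the likeliest cause. But that general pointer does not settle which text governs, since the SAP departs from Section 9 elsewhere, and no code for this model is printed. A formula is what a programmer is most likely to copy.

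Freeing h is also not uniformly better. At h=3.5 with ED50 105 mg it lowers coverage from 89% to 83%, and at h=2 with ED50 210 mg it gains almost nothing. This stands. The large and consistent loss is at h=1, which is not the shape the SAP expects.

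The coverage figures rest on assumed targets and on raw kilograms, whereas the SAP log-transforms LBM. The targets are assumptions and are shown over a range. The transform should change little, because the result depends essentially on the ratio of effect to SD.

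The tilt in the selection rule has no stated size. That is conceded: this SAP gives no target response, averaging weights or fit criterion (a programming specification not available here might), and MCP-Mod can also be displaced with h free.

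Finally, the averaging change is a separate matter with negligible effect at the planned effect sizes. That is correct. It is still an undeclared departure from the protocol.

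**Conclusion.** Both points hold. SAP 2.10.1.6 contradicts itself and protocol 9.4.4 on the Hill coefficient, and 2.14 does not cover it. The averaging rule was also changed without being listed.

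The size is conditional. If the printed equation is programmed and the true curve is shallow (h=1), the nominal 95% interval covers roughly 50–75% at a 1.0 kg effect, and 20% in the worst 2.0 kg scenario. At h=2 the loss depends on ED50, and at h=3.5 there is none. If the prose is programmed, there is no harm. The averaging change matters only for weak signals, and then to a degree set by a target response that the SAP does not state.

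These are supportive analyses feeding dose selection. The correction should be made, but it does not touch the primary test, its alpha or the sample size.

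**What to change.** 1. In SAP 2.10.1.6, print the supplementary model as E0 + Emax·d^h/(ED50^h + d^h). Estimate h within stated bounds (0.3 to 10, for example) and flag fits where h lies on a bound. Keep 3.5 only for the MCP-Mod candidate.
2. If 3.5 is really intended, remove the wording about estimating h and the 4-parameter label, and list the departure from protocol 9.4.4 in 2.14.
3. Restore averaging over models significant in the contrast test, with no target dose reported when none is significant, or declare the change in 2.14.
4. It would help, though it is not part of the defect, to state the target response, contrast level, averaging weights and fit criterion.

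The drafting cost is one equation, one sentence and one or two lines in 2.14. The statistical cost of freeing h is real. At h=1 and a 1.0 kg effect, the interval spans about 7–10 fold instead of about 3 fold. With three active doses, h is weakly identified and reaches a bound in 12–35% of trials at 1.0 kg (0–10% at 2.0 kg). Coverage stays below 95% in most 1.0 kg scenarios.

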9.2 Analysis sets

The Full Analysis Set (FAS) used for all efficacy analyses will consist of all randomized patients who received at least one dose of investigational treatment. Patients will be analyzed according to the treatment they were assigned to at randomization. Patients who entered the study before Amendment 2 will be pooled with fixed-dose patients as follow: bimagrumab 3 mg/kg patients will be analyzed as member of the 210 mg group, bimagrumab 10 mg/kg patients will be analyzed as member of the 700 mg dose group.

The safety (SAF) Analysis Set will consist of all patients who received at least one dose of study medication. Patients will be analyzed according to the treatment received. Patients who entered the study before Amendment 2 will be pooled with fixed-dose patients as detailed for the FAS.

Per-protocol (PP) Analysis Set will include all FAS patients who complete the study without major deviations from the protocol procedures. Major protocol deviations and the definition of the PP set will be identified and finalized based on blinded review of the data, prior to the data extraction for the primary analysis (EoT) and the global study team group level unblinding.

For patients who entered the study before Amendment 2 and have been treated for more than 6 months, data collected after the Week 24 visit will be listed.

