2.3 Treatment pooling and handling of pre-amendment 2 patients

Patients randomized prior to implementation of protocol amendment 2, dated 30-Jun-2015, were receiving a weight-based dose and were to be treated for 52 weeks. After consenting to protocol amendment 2, their treatment regimen was converted in a blinded manner via the Interactive Response Technology (IRT) system to a fixed-dose treatment regimen at their next scheduled visit. Patients on 3 mg/kg bimagrumab were converted in a blinded manner to 210 mg bimagrumab fixed dose and patients on 10 mg/kg bimagrumab were converted in a blinded manner to 700 mg bimagrumab.

Patients who had already completed Week 20 had their EOT (Week 24) assessments performed at their next scheduled visit after which they continued the study as per protocol amendment 2. Patients randomized prior to implementation of protocol amendment 2 may therefore have been treated for more than 24 weeks (more than 6 infusions).

Patients who entered the study prior to protocol amendment 2 will be pooled with fixed-dose patients as follows:

Table 2.1 Treatment pooling

Time of Entry into Study	Randomized	Analyzed
Prior to protocol amendment 2*	Placebo	Placebo
	Bimagrumab 3 mg/kg	Bimagrumab 210 mg
	Bimagrumab 10 mg/kg	Bimagrumab 700 mg

After protocol amendment 2	Placebo	Placebo
	Bimagrumab 70 mg	Bimagrumab 70 mg
	Bimagrumab 210 mg	Bimagrumab 210 mg
	Bimagrumab 700 mg	Bimagrumab 700 mg

*For patients who entered the study prior to protocol amendment 2 and potentially treated for more than 6 months (24 weeks).

Subsequently, for the pre-amendment 2 patients potentially treated for more than 24 weeks (more than 6 infusions), the treatment epoch, as used for analysis purposes, is defined as the first 24 weeks of treatment only i.e. start of the first infusion of study drug (Day 1) to last infusion of study drug cut-off at Week 20 + 4 weeks. Implying a total of 6 infusions within the defined 24-week treatment epoch.

Taking the aforementioned defined 24-week treatment epoch into account, the same conventions for defining treatment-emergent events (as well as assessments with clinically notable criteria defined, such as laboratory assessments, vital signs, electrocardiogram etc.) and for identifying concomitant medications will apply for all patients regardless of whether they were randomized pre- or post-amendment 2:

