[Appendix 3](#) (Data collection tool [eCRF] differences pre- and post-protocol amendment 2) details the differences in data collection pre- and post-protocol amendment 2. For variables that were only collected and recorded for patients enrolled pre-amendment 2 (N = 14) relevant data will be presented in by-patient data listings only and no further details with regards to these variables are included in the subsequent sections.

[Appendix 4](#) (Data collection tool [eCRF] differences pre- and post-protocol amendment 3) details the differences in data collection pre- and post-protocol amendment 3.

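### The supportive mg/kg sigmoidal Emax model has no baseline LBM term although mg/kg varies within each arm only through body weight, and its dose regressor is not the dose received for pre-amendment 2 infusions

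*SAP*

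**What the plan says.** SAP 2.10.1.6 adds a second dose-response model beside MCP-Mod, a sigmoidal Emax curve in mg/kg, for which "the fixed dose of 700 mg, 210 mg, and 70 mg for each patient will be normalized by their Baseline weight in kg". Protocol 9.4.4 has the same rule: "the fixed dose of 70 mg, 210 mg, and 700 mg from each patient will be normalized by their" baseline weight. Neither section gives a separate rule for patients randomised before Amendment 2.

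The population is stated for MCP-Mod, "for all patients assigned to FAS, dose-response modeling will be performed", and no other is named for the mg/kg model. The FAS includes the pre-amendment 2 patients. SAP 2.3 puts their number at 14 and says that they "were receiving a weight-based dose and were to be treated for 52 weeks". They were then "converted in a blinded manner via the Interactive Response Technology (IRT) system to a fixed-dose treatment regimen at their next scheduled visit". Protocol 9.2 pools them by nominal dose: "bimagrumab 3 mg/kg patients will be analyzed as member of the 210 mg group", and 10 mg/kg patients with the 700 mg group.

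The curve is written with a basal effect, a maximum effect, an ED50 and a Hill exponent. No covariate appears and the response scale is not stated. The primary MMRM (SAP 2.10.1.3) analyses log LBM and adjusts for log baseline LBM and its interaction with visit.

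**The concern.** The reason for a mg/kg model is to use each patient's own dose. For infusions given by weight, the stated regressor replaces a known dose with a nominal one, and the error depends on body weight.

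The second issue reaches every fixed-dose patient. Randomisation balances body size between arms, so a comparison of arms by nominal dose is protected. The mg/kg regressor also uses differences within arms, and those are not randomised: at a fixed 700 mg, a patient has a higher mg/kg dose only by being lighter. If lighter patients, who tend to have less lean mass, change by more or less than heavier ones for reasons unrelated to drug, the model has only the dose curve with which to describe it. ED50 and Hill would absorb that association. The width of this model's intervals also helps to decide whether MCP-Mod remains the default for estimating dose.

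**Working it through.** **Inputs.** Fixed doses are 70, 210 and 700 mg, from 1, 3 and 10 mg/kg at a rounded mean weight of 70 kg, with a literature mean of 66 +/- 12 kg (protocol 3.3). Minimum entry weight is 35 kg (protocol 4.1). Allocation was 1:1:1 before Amendment 2 (protocol 5.2). There are 14 such patients (SAP 2.3). Planned arms are 70/35/70/70 (SAP 2.13).

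**The plan's own conversion.** 1 x 70 = 70, 3 x 70 = 210 and 10 x 70 = 700 mg. It reproduces exactly, so the regressor equals a weight-based dose only at 70 kg.

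**Part 1: regressor against dose received.** Let m be 3 or 10 mg/kg, W the weight, and k the number of the six in-window infusions given by weight. The regressor is 70m/W. The mean received is [k x m + (6 - k) x 70m/W]/6. The relative error is their ratio minus 1, the same for both doses.

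| Weight (kg) | Regressor, 210 / 700 mg (mg/kg) | k = 1 | k = 3 | k = 6 |
|---|---|---|---|---|
| 35 | 6.00 / 20.00 | +9% | +33% | +100% |
| 54 | 3.89 / 12.96 | +4% | +13% | +30% |
| 66 | 3.18 / 10.61 | +1% | +3% | +6% |
| 70 | 3.00 / 10.00 | 0 | 0 | 0 |
| 78 | 2.69 / 8.97 | -2% | -5% | -10% |

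Every active pre-amendment 2 patient had at least the first infusion by weight. k = 6 applies to those past Week 20 at the switch: "Patients who had already completed Week 20 had their EOT (Week 24) assessments performed at their next scheduled visit". Expected active patients: 14 x 2/3 = 9.3, which is 9.3/175 = 5.3% of the planned active patients.

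Effect on the curve: 500 simulated trials with 5 affected patients in each of the 210 and 700 mg arms, all with k = 6, weight 66 +/- 12 kg, Hill 3.5, effect 1 and SD 1. Median ED50 was 1.52 with either regressor for a true value of 1.5, and 2.98 (assigned) against 2.97 (received) for a true value of 3.0. The median absolute shift was 0.01 to 0.03 mg/kg, against an interquartile range of about 0.6 to 0.8.

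**Part 2: no baseline term.** Between 78 and 54 kg (mean +/- 1 SD) the regressor runs from 0.90 to 1.30, 2.69 to 3.89 and 8.97 to 12.96 mg/kg in the three arms. Each is a factor of 78/54 = 1.44 that comes from body weight alone.

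The documents give no correlation between baseline LBM and change, so +/-0.3 is assumed. With Hill fixed at 3.5, adding baseline LBM lowered the root mean square error of log ED50 by about a quarter to a third, for example from 0.375 to 0.259 (1 - 0.259/0.375 = 31%). A repeat for this write-up used 1,000 trials per scenario, planned arm sizes, LBM = 0.65 x weight with 7% log-scale noise, effect 1 and total residual SD 1:

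| True ED50 | Correlation | RMSE without / with | Reduction | Median ED50 without / with |
|---|---|---|---|---|
| 1.5 | -0.3 | 0.325 / 0.261 | 20% | 1.66 / 1.50 |
| 1.5 | +0.3 | 0.304 / 0.265 | 13% | 1.41 / 1.45 |
| 3.0 | -0.3 | 0.388 / 0.219 | 44% | 3.20 / 3.00 |
| 3.0 | +0.3 | 0.338 / 0.249 | 26% | 2.71 / 3.00 |
| 1.5 | 0 | 0.284 / 0.286 | none | 1.50 / 1.50 |
| 3.0 | 0 | 0.250 / 0.252 | none | 3.00 / 3.00 |

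The four non-zero scenarios average (20 + 13 + 44 + 26)/4 = 26%. The term brings the median ED50 to or nearer the true value in all four. Much of the RMSE gain lies in the tails: the median absolute error fell in two of the four and rose slightly in the other two.

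With Hill estimated, results were mixed. RMSE without / with the term, in the same row order, was 0.461 / 0.309, 0.348 / 0.321, 0.529 / 0.366 and 0.371 / 0.389. Both cases matter, because the SAP text says that Hill is estimated while its printed formula has 3.5; the protocol prints h.

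**The case against.** The strongest reply is that little depends on this model. It is supportive, no hypothesis test uses it, and MCP-Mod on nominal dose is the default if it fits well and gives narrower intervals. The pooling is deliberate and disclosed, and efficacy is also presented before and after Amendment 2. All of this stands, and it limits the point to a minor one. The amendment subgroup presentation is not stated for this model, however.

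A reader might infer that the pre-amendment doses distort the fitted curve, or that these patients have the wrong dose throughout. The documents do not support either. After the switch the regressor matches the dose given, placebo patients are unaffected, the error at 66 kg is at most +6%, and ED50 barely moved in a severe simulated case. The +100% figure needs a patient at the 35 kg entry limit with all six infusions by weight.

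On the baseline term, the SAP gives only a mean function and does not rule out covariates. On the log scale the argument that smaller patients have fewer kilograms to gain largely disappears. A simulation with a purely proportional 2.5% gain and Hill fixed at 3.5 gave median ED50 of 1.41 on the kg scale without the covariate, 1.44 with it and 1.48 on the log scale (true 1.5); for a true 3.0 the values were 3.04, 3.06 and 3.04. That supports using the log scale. It does not cover a baseline-change association that remains on that scale, such as regression to the mean, which the primary model already adjusts for.

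**Conclusion.** Both parts hold as minor points about a supportive analysis.

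The regressor is misdefined for pre-amendment 2 infusions in about 9 expected active patients, by +30% to -10% between 54 and 78 kg at worst, with negligible effect on the fit. The actual arm split, weights and switch times are not in the documents, so these are ranges.

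The missing baseline term matters more, because it concerns all fixed-dose patients and the within-arm dose variation is body weight alone. Its size rests on an assumed correlation: none at zero; about a quarter to a third less ED50 error at +/-0.3 with Hill fixed at 3.5, ranging from 13% to 44% over the scenarios tabulated; mixed when Hill is estimated. A reader might go further and infer that the dose chosen for later development would be wrong. The documents do not support that, since MCP-Mod is the default and the correlation is unknown. The primary and secondary tests are untouched.

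**What to change.** In SAP 2.10.1.6, for the mg/kg model:

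- Define the regressor as the mean mg/kg received per infusion within the 24-week treatment epoch. Use the assigned 3 or 10 mg/kg for infusions before the switch and fixed mg divided by baseline weight after it. Alternatively, keep the present rule and repeat the model without the pre-amendment 2 patients.
- State that the response is change in log total LBM, and add log baseline total LBM as a covariate on E0, in line with the primary MMRM.
- State whether Hill is estimated or fixed at 3.5, so that text and formula agree.

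The cost is SAP wording, one variable derived from the dosing records and IRT data already held, and one extra parameter. No new data are needed, and no primary or secondary test changes. Leaving out the 14 patients would settle the first part only.
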